Two study groups will be formed, a control and an intervention group receiving the integrated package of interventions.

The activities of the control and intervention group are summarized in Table 1.

Table 1: Description of Prevention, Screening, Treatment, and Relapse Prevention Activities in the Control and Intervention Groups

	Control*	Mali Intervention
Prevention		
Usual NASG activities (Home visits and group counselling on nutrition and health)	X	X
Integrated NASG (or intensive)		
- NASG created proportionate to population size of village	X	
- Frequent home visits (once a month)	X	
- Strengthening of group counselling / cooking demonstrations activities	X	
- Distribution of SQ-LNS to 6-17-month children	X	
Screening		
Usual activities of the NASGs (screening using MUAC criterion during home visits and group counselling)	X	X
Family MUAC		X
Screening with Weight-for-height / MUAC during the 7th month of the IRAM project	X	X
Treatment		
National CMAM Program (CSCOM and CHW Site)	X	X
Integrated NASG (or intensive)		

Follow-up of cases under treatment by intensive home visits (twice a month)	X
Relapse prevention	
Integrated NASG (or intensive)	
-Intensive home visits (twice a month)	X
-Distribution of nutritional supplements to 6–24-month children post-treatment	X

*In Koutiala villages, NASGs were created by the health district and UNICEF in 2019. However, their monitoring was stopped in 2019. It is not known at this time whether the NASGs are still operational.

The study was designed as a two-arm, cluster-randomized, nonblinded effectiveness study. A cluster-randomized design was used because individual randomization of the NASG intervention was not feasible. A cluster was defined as the catchment area of a first-line health center. All health center catchment areas included in the study were first grouped into 4 strata according to their characteristics to obtain a more balanced randomization result.

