Considering a baseline longitudinal prevalence of 13.2% (obtained from the control group of the PROMIS Mali study) with a standard deviation (SD) of 0.239 for the control group and an SD of 0.189 for the treatment group, a mean cluster size of 55 (anticipating a loss of follow-up of 15%), a statistical power of 80%, a type I error of 5% and an intra-cluster coefficient of 0.04, we need at least 42 clusters to detect a minimum difference of ~ 4.55 percentage points, , which is equivalent to a relative risk of 0.65.

Cohort 2 - Primary Outcome: recovery Rate

The aim is to include all URENAS and URENAM treatment data for children between 6 and 23 months of age. Using 2019 health district statistics, the total number of SAM and MAM cases (6-23 months of age) over 8 months of follow-up was estimated at 750 and 1,000 respectively.

Scenario with 45 clusters available (SAP version 1.0)

With 44 clusters that each have an average of 35 cases of SAM and MAM over a 7-month period, assuming a URENAS/URENAM cure rate of 79%, a statistical power of 80%, a type I error of 5% and an intra-cluster coefficient of 0.05, a minimum difference of ~9.0 percentage points in the URENAS/URENAM cure rate could be detected in children aged 6-23 months.

Scenario with 42 clusters available (SAP version 2.0)

With 42 clusters that each have an average of 50 cases of SAM and MAM over a 7-month period, assuming a URENAS/URENAM cure rate of 79%, a statistical power of 80%, a type I error of 5% and an intra-cluster coefficient of 0.05, a minimum difference of ~9.0 percentage points in the URENAS/URENAM cure rate could be detected in children aged 6-23 months.

Cohort 3 - Primary Outcome: Prevalence of Relapse

Scenario with 45 clusters available (SAP version 1.0)

We considered a 35% prevalence of relapse in children aged 9-17 months, three months after treatment completion (estimate obtained in the control group of the PROMIS Mali study). We need a minimum of 44 clusters with a mean cluster size of 20 (anticipating a 15% loss of follow-up), a statistical power of 80%, a type I error of 5% and an intra-cluster coefficient of 0.04 to detect a minimum difference of ~ 12.0 percentage points in the 9-18⁵ months age group.

Scenario with 42 clusters available (SAP version 2.0)

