⁹ Balegamire S, Siling K, Alvarez JL, Guevarra E, Woodhead S, Norris A. 2015. "A Single Coverage Estimator for Use in SQUEAC, SLEAC, and Other CMAM Coverage Assessments." *Field Exchange*, vol. 49

¹⁰ Barba, Francisco M., Lieven Huybrechts, and Jef L. Leroy. 2020. "Incidence Correction Factors for Moderate and Severe Acute Child Malnutrition From 2 Longitudinal Cohorts in Mali and Burkina Faso." *American Journal of Epidemiology* 189(12): 1623–27

used to assess the impact of the program. For cohort 3, data from October 2021 to February 2022 will be used to study the impact of the intervention on relapse.

Guiding principles and analysis strategy

Data will be analyzed on intent-to-treat basis. To allow for an analysis “as randomized” in the presence of missing data, we will impute missing data of the primary outcomes of the longitudinal study using a multiple imputation strategy under the *missing at random* assumption. Data management, data cleaning, and statistical analyses will be done using Stata 17.0 (Statacorp, USA). The statistical significance will be set at 5%. All statistical tests will be two-sided. The analysis of primary study outcomes will not be adjusted for multiple testing (n=3 primary study outcomes) given the data involved represent three distinct experimental and control study arms with each one primary study outcome.

We present results from non-adjusted and adjusted linear mixed effects regression models. The non-adjusted models use *health center catchment area* as a random intercept and sampling stratum as a fixed effect to represent the study design. Adjusted regression models further include as fixed effects the cluster baseline means (May-July 2021 period) of the outcome under analysis, month of enrollment into the study (cohort effect), child sex, child age, and primiparity. Furthermore, if any baseline household, caregiver or child characteristic is imbalanced (absolute difference of ~5pp) between study groups, we conduct an additional robustness analysis adjusting the analysis for this covariate.

Cohort 1 specific considerations

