Studying effect modification of an intervention offers important insights in the mechanism of a possible impact. In this study, we applied a stratified cluster randomized sampling, stratifying by health center catchment area characteristics (urban/rural, proportion of population living >15km from a health center, previous activities on child nutrition delivered by World Vision Mali). To gain more operational insight on how the intervention performed according to stratum characteristics we will assess possible effect modification of the intervention by these strata. Given that these tests are explorative in nature, we assess

interaction terms at a statistical significance set at 10%. Statistical models are the same as described in earlier sections. Results from both adjusted and non-adjusted regression models will be presented. If there are indications of effect modification by stratum characteristics, we will present impact results stratified by stratum.

Sensitivity analyses

We will assess whether impacts on primary outcomes in cohort 1 and 3 are sensitive to the definition of wasting, by assessing impact on wasting prevalence and incidence when wasting is defined with 2 alternative definitions: 1) MUAC < 125 mm or oedema, and 2) WLZ < -2 Z-scores or oedema.

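### Stratum-specific results are tied to a weak 10% interaction test, so the between-stratum contrasts that get displayed are exaggerated; report them for every primary outcome whatever the p-value

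*SAP*

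**What the plan says.** The SAP's Study design section says that the health center catchment areas were "first grouped into 4 strata according to their characteristics" before randomization. The Effect modification section, under Considerations for analysis, plans to test whether the intervention effect differs by stratum, to learn operationally how the package performed in different kinds of area.

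- **Status and level.** The section opens its rule with "Given that these tests are explorative in nature, we assess" and sets the test for "interaction terms at a statistical significance set at 10" percent. The Guiding principles section adds: "All statistical tests will be two-sided".
- **Unconditional reporting.** "Results from both adjusted and non-adjusted regression models will be presented".
- **Conditional reporting.** "If there are indications of effect modification by stratum characteristics, we will present impact results stratified by stratum".

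The section does not define what counts as an indication; the 10% test is the only candidate. It speaks once of modification by the strata and once of modification by stratum characteristics, which are different tests. It gives neither stratum sizes nor an expected size of interaction.

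**The concern.** Showing stratum estimates only after a significance test filters what readers see. If the test has little power, an interaction has to be overestimated to pass, so the contrasts displayed are larger on average than the true ones. When the test is not met, nothing commits the authors to show the stratum estimates, and a reader cannot tell no modification from modification estimated too imprecisely to detect. The section exists to give operational insight, and the stratum estimates are what would give it.

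The double wording adds a choice. A single test of the four-level stratum has 3 degrees of freedom. Testing characteristics one at a time gives three tests per outcome. Three two-level criteria could define 2 × 2 × 2 = 8 cells, but only four strata were formed, so the characteristics cannot be fully separated from one another.

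**Working it through.** **Inputs (SAP, Sample Size, cohort 1, 42-cluster scenario).** Control longitudinal prevalence 13.2%; SDs 0.239 and 0.189; mean cluster size 55; ICC 0.04; 80% power; 5% two-sided. Assumed: 21 clusters per arm. The calculation is on the risk-difference scale.

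**1. Reproduce the plan's figure.** The SAP states: "we need at least 42 clusters to detect a minimum difference of ~ 4.55 percentage points".
- Design effect = 1 + (55 − 1) × 0.04 = 3.16.
- SE = √[(0.239² + 0.189²) × 3.16 / (21 × 55)] = √[0.09284 × 3.16 / 1155] = 1.59 points.
- Detectable difference = 2.80 × 1.59 = 4.47 points (normal), or 4.58 points (t with 40 df). The stated 4.55 lies between, so it reproduces.
- Working back from the stated figure: SE = 4.55 / 2.80 = 1.62 points. I use 1.62 below; 1.59 changes nothing material.

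**2. Power of the 10% test and inflation of what passes.** For a two-level modifier with a share f of the areas, SE of the interaction = 1.62 / √[f(1 − f)], that is 3.25 points at f = 0.5 and 4.55 points at f = 0.15. The critical value is 1.645. Inflation is the mean absolute estimate among significant results, divided by the true value.

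| True interaction | Split | Power | Inflation |
|---|---|---|---|
| 4.55 points | 50/50 | 40% | 1.7 |
| 4.55 points | 15/85 | 26% | 2.2 |
| 2.3 points | 50/50 | 18% | 3.1 |
| 9.1 points | 50/50 | 88% | 1.1 |
| 9.1 points | 15/85 | 64% | 1.3 |

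Power reaches 50% at 1.645 × 3.25 = 5.3 points (even split). It reaches 80% at (1.645 + 0.842) × 3.25 = 8.1 points, against a control prevalence of 13.2%.

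**3. Joint test over four equal strata (assumed).** SE per stratum = 1.62 × √4 = 3.25 points; 95% CI half-width = 1.96 × 3.25 = 6.4 points. I simulated sets of four estimates around a uniform effect of −4.55 points and compared the heterogeneity statistic with the 90th percentile of chi-square on 3 df.
- Tests that pass: 10%.
- Mean spread, highest minus lowest stratum, when the test passes: 12.1 points. Over all sets: 6.7 points. True spread: 0.
- Mean of each stratum's estimate when the test passes: −4.5 to −4.6 points, so still centered on the common effect.
- At least one stratum on the harm side: 75% of sets that pass, which is 0.10 × 75% = 7.5% of all outcomes under the conditional rule. If all strata are always shown: 1 − [Φ(4.55/3.25)]⁴, about 28%.

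**4. False signals when there is no modification.** One joint test for each of three primary outcomes: 1 − 0.9³ = 27%. Three characteristics for each of three outcomes: 1 − 0.9⁹ = 61%. Both assume independent tests.

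**The case against.** **Exploratory status.** The modifiers are the design strata, fixed in advance. The tests are declared exploratory, and the 10% level is a deliberate relaxation to gain power. No primary estimate or conclusion depends on this section. All of that stands, and it keeps the point modest. But an exploratory label does not undo selective display.

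**Does the rule pick out exaggerated strata?** A reader might infer so. It does not: once the condition is met, every stratum for that outcome is shown, and step 3 finds no directional bias in any of them. Only the spread between strata is exaggerated.

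**Does most real modification stay hidden?** This too might be inferred, but it depends on an effect size that the SAP does not give. It is true below about 5.3 points at an even split and false for an interaction of 9.1 points. The text does not say that stratum results appear only on a significant test. The unconditional promise to present both sets of models can also be read as covering the interaction models. What may go unreported is the stratum estimates, not necessarily the test.

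**Will the rule tend to publish false patterns?** Two figures could suggest this. The 75% with a stratum on the harm side applies only to outcomes that pass; per outcome it is 7.5%, lower than the 28% if everything is always shown. The 61% needs nine independent tests, whereas tests of overlapping characteristics are not independent; with one joint test per outcome the figure is 27%. The case for always showing the strata is that it removes selection, not that it produces fewer odd-looking strata.

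**Conclusion.** The point holds in a limited form. The only stated trigger for showing stratum results is a test that, at cohort 1 precision, misses an interaction as large as the whole detectable main effect more often than it finds it (power about 40% at an even split, 26% at 15/85). Contrasts that pass are inflated about 1.7 and 2.2 times. Under a uniform effect, selection nearly doubles the displayed spread, from about 7 to about 12 points. The test itself is also not uniquely specified.

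The figures assume 21 clusters per arm and equal strata or the splits named. They use normal approximations on the risk-difference scale, whereas the planned primary model for cohort 1 is Poisson, so they are approximate. Nothing was computed for cohorts 2 and 3. This is a cheap improvement to an exploratory section; the main analysis is not at fault.

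**What to change.** In the Effect modification section:

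1. Specify one joint arm-by-stratum test (3 df) for each primary outcome, and remove the alternative wording by characteristic.
2. Replace the conditional sentence with a commitment to present all four stratum estimates and the interaction estimate, each with a 95% CI, whatever the p-value.
3. Label the display exploratory and state that it is to be read against the overall effect.

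Restricting the section to the primary outcomes is optional.

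**Cost.** SAP wording and three small tables or forest plots; no new data. The change removes selection but adds no precision: with four equal strata each cohort 1 estimate carries a 95% CI of about ±6.4 points. About 28% of outcomes with a uniform effect of −4.55 points would show at least one stratum on the harm side by chance, so the intervals and the label are essential.
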